1.2 BACKGROUND ON EPOETIN BETA (RECORMON®)

Recormon® (epoetin beta) is a sterile, purified, stable recombinant human erythropoietin concentrate produced from genetically engineered Chinese hamster ovary (CHO) cells containing a cloned human erythropoietin gene. Recormon® is provided as lyophilisate and solvent for solution for injection in cartridge, and as solution for injection in pre-filled syringes. The reconstituted product is a colorless, clear to slightly opalescent solution.

Epoetin beta is a glycoprotein that stimulates the proliferation and differentiation processes of the erythroid stem cell compartment and also has a stimulatory effect on the proliferation and maturation compartment of the erythron. Epoetin beta therefore leads to an increase in haemoglobin formation and an associated acceleration of cell maturation with reduction in the cell cycle time. A further effect of epoetin beta is the acceleration of reticulocyte maturation and an increase in the release of reticulocytes into the bloodstream.

Recormon® has been approved by Thai FDA for the following therapeutic indication(s)

- Treatment of symptomatic anemia associated with chronic kidney disease (CKD) in patients on dialysis.
- Treatment of symptomatic renal anemia in patients not yet undergoing dialysis.
- Prevention of anemia of prematurity in infants with a birth weight of 750 to 1500 g and a gestational age of less than 34 weeks.
- Treatment of symptomatic anemia in adult patients with non-myeloid malignancies receiving chemotherapy.
- Increasing the yield of autologous blood from patients in a pre-donation program.
- Its use in this indication must be balanced against the reported increased risk of thromboembolic events. Treatment should only be given to patients with moderate anemia (Hb 10 - 13 g/dL [6.21 - 8.07 mmol/l], no iron deficiency) if blood conserving procedures are not available or insufficient when the scheduled major elective surgery requires a large volume of blood (4 or more units of blood for females or 5 or more units for males).
- Treatment of symptomatic anemia associated with Myelodysplastic Syndromes (MDS) patients, including other ineffective erythropoiesis

See the local prescribing information for more details.

1.3 STUDY RATIONALE AND BENEFIT–RISK ASSESSMENT

Chronic refractory anemia and long-term use of blood transfusions pose a tremendous clinical and economic burden to the management of MDS patients. Thus, treatment options aimed at maintaining transfusion independence or delaying transfusion dependence play an important role in the management of low-risk early disease.

Of the currently available therapeutic options, Erythropoiesis-stimulating agents (ESAs) alone or in combination with GCSF appear to fulfill this goal in a significant proportion of MDS patients. In contrast to the application of these growth factors to treat the side effects of chemotherapy in other cancers, their use in MDS appears to serve a therapeutic role since ineffective hematopoiesis, and specifically defective erythropoiesis, constitute the basic pathology in MDS. By promoting survival and differentiation ESAs overcome excessive apoptosis of erythroid progenitors and, hence, are therapeutic in alleviating the basic pathology of these disorders.

Recombinant erythropoietin (EPO) can correct anaemia in about 20% of MDS when used alone and 40% when combined with recombinant human granulocyte colony-stimulating factor (G-CSF), and the response rate to EPO + G-CSF is higher than that of symptomatic treatment (Economopoulos et al. 1999, Remacha et al. 1999, Hellstrom-Lindberg et al. 2003, and Casadevall et al. 2004). Major prognostic factors for a favourable response to EPO ± G-CSF are low endogenous serum EPO levels (<200 or 500 U/l) and relatively low transfusion requirement. In patients with a serum EPO level below 500 U/l, response rates to EPO + G-CSF reach 60% (Hellstrom-Lindberg et al. 2003 and Casadevall et al. 2004).

Result from prospective randomized phase III trial by the Eastern Cooperative Oncology Group (E1996) confirm earlier studies by demonstrating the efficacy of adding G-CSF to EPO and higher EPO dose for enhancing erythroid responses in MDS (Greenberg et al. 2009). Mo yo et al. (Mo yo et al. 2007) also suggest increasing EPO dose may have a greater impact on erythroid responses than addition of G/GM-CSF.

Three ESAs have been used in MDS, epoetin- α and darbepoetin- α in the USA, and in addition epoetin- β outside of the USA. Several studies have proven the efficacy of these ESAs in eliciting erythroid response in low/int-1 MDS patients (MundLe 2006). A pretherapy endogenous serum erythropoietin (sEPO) level of less than 500 mU/ml and transfusion requirement of less than two units/month appear to predict the best response to ESA therapy, particularly in low/int-1 disease. As reviewed previously, with the use of these criteria for patient selection and that of the standardized response evaluation criteria recommended by the International Working Group in MDS, erythroid response rates have significantly improved to nearly 60–65% from approximately 20% in the past with their earlier use in unselected all-comer MDS patients evaluated for response with variable criteria (MundLe 2006). The responses to ESA alone, or in combination with granulocyte colony-stimulating factor (GCSF), appear to be remarkably durable with a median of 23 months in the absence of transfusions (Jadersten et al. 2005). The responses are observed both in transfusion-dependent patients in terms of transfusion avoidance and Hb improvement, as well as in transfusion-independent patients in terms of Hb improvement.

It is evident that complete transfusion independence is achieved in 30–50% of patients, with a noticeable decrease in the mean number of PRBC units required to maintain Hb in others.

To date, no treatment-related side effects have been noted with ESA therapy and treatment with ESAs appears to be well-tolerated. In fact, the only largest randomized placebo-

Recormon—F. Hoffmann-La Roche Ltd

Protocol ML29005, Version 3.0 dated 12 Sep 2016

21

controlled trial with ESA in MDS conducted thus far showed that the patients treated with EPO as a single agent had numerically lower rates of adverse events (32%) compared with those on placebo (43%) (ITALIAN COOPERATIVE STUDY GROUP 1998). Furthermore, encouragingly, no treatment-related episodes of thrombosis or seizures were reported in this trial or even after long-term administration of EPO to MDS patients in another large, single-arm trial (Terpos et al. 2002). The noticeable absence of therapy-related thrombotic events with EPO treatment of MDS in several clinical trials so far is indeed distinguished from even the minimum acceptable risk of thrombotic complications of ESAs when used in chemotherapy-induced anemia as listed in the drug prescribing information for epoetin- α or darbepoetin- α . Thus, treatment of MDS with ESA in general seems to be well tolerated with significant clinical benefits in MDS.

ESA use in MDS is widespread; recent estimates suggest that 60% of MDS patients received ESAs (Sekeres et al. 2008). The last update of the 2011 National Comprehensive Cancer Network guidelines (Greenberg et al. 2011) acknowledges the fact that anemia is a major issue in MDS patients to be addressed even more carefully than in the past with parallel statements by the Italian Society of Hematology (Alessandrino et al 2002), the United Kingdom (UK) MDS Guidelines Group (Bowen et al. 2003), Nordic MDS Group (Guideline by NMDS group), and the Thai MDS study group (Guideline by The Thai Society of Hematology).

As improvements in haemoglobin are usually noted 6–8 weeks after initiation of an adequate dose of ESA, a minimum 8-week therapeutic trial was considered to be indicated. Moreover, it should be noted that ESA doses found to impact the anemia of MDS are substantially higher than those used in chronic renal insufficiency (Oliva et al. 2010). The addition of granulocyte colony-stimulating factor (G-CSF), thought to synergize with ESA in producing an erythropoietic effect in MDS patients, is suggested for patients who do not manifest a response to ESA (Jadersten et al. 2008 and Hellstrom-Lindberg et al. 2003).

The relative durable clinical benefits and lack of adverse effects on survival or rate of leukemic transformation may uniquely position ESAs as the eminent therapeutic choice. Importantly, the subset of MDS patients benefiting from ESA therapy is now well defined as the low-/int-1-risk group with sEPO of less than 500 mU/ml and a PRBC transfusion need of less than two units/month. From a benefit–risk perspective, the positive long-term outcomes demonstrated with ESAs in a specified group of MDS patients have yet to be shown with other therapies. ESAs thus remain a treatment of choice for low-/int-1 MDS patients when considered against the significant risks and estimated high costs associated with complicated chronic blood transfusions.

However, the majority of clinical studies of ESAs in MDS patients use EPO- α . Few data have been published for EPO- β . This prospective study aim to provide the additional effectiveness and safety profile of Recormon® (EPO- β) for treatment of symptomatic anemia associated with MDS patients for all epoetin formulations review by Thai FDA.

2. OBJECTIVES

2.1 EFFICACY OBJECTIVES

The primary efficacy objective for this study is:

- To assess the efficacy of Recormon® for treating anemic patients with low/intermediate-1 risk MDS, as measured by erythroid response

2.2 SAFETY OBJECTIVES

The safety objective for this study is:

- To assess the safety of Recormon® for treating anemic patients with low/intermediate-1 risk MDS

3. STUDY DESIGN

3.1 DESCRIPTION OF STUDY

3.1.1 Overview of Study Design

This is a phase IV, prospective, multi-centre, open label study to assess the efficacy of Recormon® for treating anemic patients with low/intermediate-1 risk MDS, in approximately 120 adult patients. The primary efficacy endpoint is a proportion of patients achieving erythroid response at week 12 according to IWG 2006 definition. The trial will be conducted at approximately 8 centres nationwide.

All potential study patients must provide signed written informed consent approved by the relevant independent Ethics Committee before undergoing any study-specific procedures. Results of the screening assessments must be available and patients must meet all eligibility criteria prior to enrolment into the study. The study design is shown in Figure 1.

[figure not shown]

Figure 1 Study Scheme

The study consists of a 2-week screening period, a 12-week treatment phase and end-of-study visit (see figure 1). After screening, eligible patients will be treated with epoetin beta (Recormon®) as recommended in the approved label and international guidelines for the use of epoetin in MDS patients, Recormon® dosage will be adjusted on the basis of erythroid response.

During screening period, serum level of endogenous erythropoietin will be assessed, as well as liver and kidney function. Bone marrow morphology analysis and karyotyping are also performed during screening if they have not been assessed in the 6 months prior to participation in the study. Complete blood count test is performed during screening period and at every patient's visit until the end of study visit. The result should be available prior to dosing of Recormon®.

The patient's erythroid response will be assessed at week 4 and every 4 weeks thereafter, until end-of-study visit. Patients who achieve Hb level ≥ 12 g/dL will stop treatment, while

Recormon—F. Hoffmann-La Roche Ltd

Protocol ML29005, Version 3.0 dated 12 Sep 2016

23

patients with Hb level < 12 g/dL will continue treatment for the total of 12 weeks. Concurrent G-CSF can be administered upon physician discretion.

Patients can withdraw from the study at any time as per section 4.5.1

Study oversight will be assured by a steering committee to guide study conduct, to review the results at the end of the study, to approve and sign-off the study report and to prepare and submit a publication to a peer-review journal. The steering committee will be made up of investigators and Roche representatives and will meet at regular intervals.

A schedule of assessments is provided in Appendix 1.

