The study consists of a 2-week screening period, a 12-week treatment phase and end-of-study visit (see figure 1). After screening, eligible patients will be treated with epoetin beta (Recormon®) as recommended in the approved label and international guidelines for the use of epoetin in MDS patients, Recormon® dosage will be adjusted on the basis of erythroid response.

During screening period, serum level of endogenous erythropoietin will be assessed, as well as liver and kidney function. Bone marrow morphology analysis and karyotyping are also performed during screening if they have not been assessed in the 6 months prior to participation in the study. Complete blood count test is performed during screening period and at every patient's visit until the end of study visit. The result should be available on visit date, prior to the Recormon® administration

The patient's erythroid response will be assessed at week 4 and every 4 weeks thereafter, until end-of-study visit. Patients who achieve Hb level ≥ 12 g/dL will stop treatment, while patients with Hb level <12 g/dL will continue treatment for the total of 12 weeks. Concurrent G-CSF can be administered upon physician discretion.

Number of Patients

120 patients expected to be enrolled.

Target Population

Adult anemic MDS patients (≥ 18 years old) in the low or intermediate-1 risk group according to the International Prognostic Scoring System (IPSS)

Inclusion Criteria

Patients must meet the following criteria for study entry:

1. Able and willing to provide written informed consent and to comply with the study protocol
2. Adult patients (≥ 18 years old)
3. Low or intermediate-1 risk MDS (having IPSS risk score ≤ 1) confirmed with bone marrow morphology analysis and karyotyping within 6 months prior to screening
4. No previous treatment with hematopoietic growth factors within 3 months prior to screening
5. Symptomatic anemia ($Hb < 10$ g/dL) as determined by investigator
6. Serum Erythropoietin < 500 mU/ml within 14 days prior to the first dose of study treatment.
7. Require no red blood cell transfusion or dependent on < 4 units within 8 weeks prior to screening
8. Clinically stable for at least one month prior to entry into the study as determined by investigator

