- Absolute increase of $\geq 30 \times 10^9/L$ for patients starting with $> 20 \times 10^9/L$ platelets (Increase from $< 20 \times 10^9/L$ to $> 20 \times 10^9/L$ and by at least 100%)
- % patients with neutrophil response (pre-treatment $< 1.0 \times 10^9/L$) at week 12 defined by IWG 2006 as following;
- At least 100% increase and an absolute increase $> 0.5 \times 10^9/L$

Safety Outcome Measures

The safety outcome measures for this study are as follows:

- Tolerability and safety of Recormon®

Investigational Medicinal Products

Injectable solution of Recormon® (provided free of charge by Roche) 30,000 or 60,000 IU per week administered subcutaneously

The initial dose is 30,000 IU per week administered subcutaneously

- Response will be firstly evaluated at week 4 (visit 2):
 - If haemoglobin level ≥ 12 g/dL at any time, Recormon® should be discontinued until Hb levels are ≤ 10 g/dL
 - If the haemoglobin level increases < 1 g/dL from screening level and haemoglobin level < 12 g/dL, a 60,000 IU weekly of Recormon® will be administered subcutaneously until week 12
 - If the haemoglobin level increases ≥ 1 g/dL from screening level and haemoglobin level < 12 g/dL, a 30,000 IU weekly of Recormon® will be continued until week 12

Non-Investigational Medicinal Products

Upon physician discretion, G-CSF can be used concurrently

Statistical Methods

Descriptive statistics will be used for baseline characteristics. The interim data analysis will be performed when the first 30 patients completing 12-week treatment period.

Determination of sample size

Sample size based on a 5% significance level and the 80% power with 10% drop out resulting of 120 patients in total.

Safety: Assuming a 10% withdrawal rate, 120 patients will be enrolled such that we expect 108 patients will not withdraw and will remain evaluable. With 108 evaluable patients in this study, the sample size is sufficient to have at least 95% probability of observing a particular adverse event in at least one patient in this study, if the true proportion of patients in the target population as a whole who experience this event is 0.0274 i.e. approximately 1 in every 37 patients.

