3.2 END OF STUDY

The end of the study is defined as the date when the last patient, last visit (LPLV) occurs, that is when the last patient reaches the end-of-study visit (approximately 4 months after the last patient is enrolled). The end-of-study visit will occur 4 weeks after patient's last dose of study treatment, or earlier, if one of the following is documented for all treated patients: withdrawal from the study, loss to follow up or death.

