4.2.2 Dosage, Administration and Compliance

4.2.2.1 Dosage and administration of Recormon®

Injectable solution of Recormon® 30,000 or 60,000 IU per week administered subcutaneously

The initial dose is 30,000 IU per week administered subcutaneously

Response will be firstly evaluated at week 4 (visit 2):

- If haemoglobin level reaches ≥ 12 g/dL at any time, Recormon® should be discontinued until Hb levels are ≤ 10 g/dL
- If the haemoglobin level increases < 1 g/dL from screening level and haemoglobin level < 12 g/dL, a 60,000 IU weekly of Recormon® will be administered subcutaneously until week 12.
- If the haemoglobin level increases ≥ 1 g/dL from screening level and haemoglobin level < 12 g/dL, a 30,000 IU weekly of Recormon® will be continued until week 12

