4.4.2.2 Assessments during Treatment

All assessments must be performed on the day of the specified visit (V1 – V4), unless a time window is specified in the schedule of assessments (see Appendix 1). Assessments scheduled on the visit date should be performed prior to administration of study treatment, unless otherwise noted in the schedule of assessments.

At each treatment visit, patients will undergo the following assessments:

- Physical examination and measurements of vital signs
- Routine laboratory tests (see section 4.4.1.4 for details about individual laboratory assays). The results from these tests should be available on visit date prior to the Recormon® administration.
- AE recording
- Recording concomitant treatments and therapies
- Recording RBC transfusion needed from previous visit
- Recormon® dose adjustment will be performed at week 4±1 (see section 4.2.2.1 for details about dose adjustment)

Please see Appendix 1 for the schedule of assessments performed during the treatment period.

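### The protocol gives both a stop rule and a hold rule at Hb ≥ 12 g/dL, and does not say that patients off drug for this reason stay in the study through week 12

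*Protocol*

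**What the plan says.** **Stop.** Protocol Section 3.1.1 says: "Patients who achieve Hb level ≥ 12 g/dL will stop treatment". The synopsis, under Description of Study, has the same sentence and contrasts these patients with the rest: "while patients with Hb level <12 g/dL will continue treatment for the total of 12 weeks". Neither place mentions a restart or refers to the dosing section.

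**Hold.** The synopsis, under Investigational Medicinal Products, says: "If haemoglobin level ≥ 12 g/dL at any time, Recormon® should be discontinued until Hb levels are ≤ 10 g/dL". Section 4.2.2.1 and Appendix 1 footnote f give the same rule. Section 4.4.2.2 sends sites there: "see section 4.2.2.1 for details about dose adjustment".

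**End-of-study visit.** Section 3.2 says: "The end-of-study visit will occur 4 weeks after" the patient's final dose. Section 4.4.2.3 sets the same interval. Appendix 1 prints week 15 for this visit and attaches footnote a, which sets four weeks from the last administration after early discontinuation.

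**Visits in between.** Appendix 1 lists V3 (week 8) and V4 (week 12), each with a blood count, and attaches its Hb ≥ 12 g/dL footnote to the drug-dispensing row only. Section 3.1.1 adds: "erythroid response will be assessed at week 4 and every 4 weeks thereafter, until end-of-study visit".

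**The concern.** There are two linked problems.

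1. **Treatment.** One site could stop a patient for good at Hb ≥ 12 g/dL while another restarts at Hb ≤ 10 g/dL. Hemoglobin at week 12 would then follow different treatment in patients with the same course.
2. **Follow-up.** If the end-of-study visit is counted from the last dose actually given, a patient taken off drug early could leave before the primary endpoint is assessed. Entry requires Hb < 10 g/dL, so a patient at 12 g/dL or more has risen by more than 12 − 10 = 2 g/dL, past the 1.5 g/dL response threshold. These are the clearest hemoglobin responders. Appendix 3 also heads its improvement criteria with a duration of at least 8 weeks, and an exit near week 7 leaves about 7 − 4 = 3 weeks of observation after V2.

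How an earlier rise, the word cumulative in Section 3.4.1 and the duration criterion are applied is for the SAP. The SAP cannot recover a value that was never collected.

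**Working it through.** **Inputs**
- Dosing is weekly (Section 4.2.2.1), with the first dose at week 0 (Appendix 1, V1).
- The blood count is known before the dose: "The result should be available prior to dosing of Recormon" (Section 3.1.1). The dose due at the visit that shows Hb ≥ 12 g/dL is therefore not given.
- V2, V3 and V4 are at weeks 4, 8 and 12, each ± 1 week. End of study is at week 15 ± 1 week (Appendix 1).
- The end-of-study visit is last dose + 4 weeks (Sections 3.2 and 4.4.2.3).
- Assumption: a full course is 12 weekly doses, at weeks 0 to 11. Appendix 1 fits this, since drug is dispensed at V1, V2 and V3 but not at V4.

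**Reproducing the plan's own figure.** For a full course, 11 + 4 = week 15, as Appendix 1 prints. The last-dose rule and the schedule agree.

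**Off drug from V2, never restarted**
- Nominal: last dose at week 3, end of study at 3 + 4 = week 7.
- With V2 at weeks 3 to 5: last dose at weeks 2 to 4, end of study at weeks 6 to 8. Adding the visit's own ± 1 week gives weeks 5 to 9.
- V4 falls at weeks 11 to 13, so end of study comes first in every case. Nominally it also precedes V3 (week 8), the first scheduled count after V2 at which a restart could be decided.

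**Off drug from V3, never restarted.** The last dose is at week 7 and end of study at 7 + 4 = week 11. That lies inside V4's window, and a blood count is taken at that visit, so this case adds little.

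**Which timing governs for a patient off drug from V2**

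| How the patient is classed | Sections 3.2 and 4.4.2.3 | Appendix 1 | Conflict |
|---|---|---|---|
| Early discontinuation | about week 7 | about week 7 (footnote a) | none, but before V4 |
| On hold, not restarted | about week 7, read literally | V3, V4 and week 15 | yes |
| On hold, restarted and dosed to week 11 | week 15 | week 15 | none |

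The text does not say whether the first or the second row applies. The dosing rule uses the word discontinued, which is also the term in Section 4.5.1.1, where patients who come off drug prematurely are asked back for the end-of-study visit. The reasons listed there do not name Hb ≥ 12 g/dL, but that list is not exhaustive.

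**The case against.** The strongest reply is that the stop sentence is loose summary wording. It does not say permanently. Every place that instructs dosing gives the hold, and Section 4.4.2.2 directs sites to Section 4.2.2.1, so a site that doses from that section has one rule. On timing, no dose is known to be the last while a restart remains open, so a hold need not trigger the four-week count. Restarting at Hb ≤ 10 g/dL requires continued hemoglobin checks. Appendix 1 schedules V3 and V4 for everyone and ties its Hb footnote to dispensing only.

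Much of this stands. It makes the hold the likelier practice and an exit near week 7 unlikely. It does not remove the inconsistency: the contrast with patients who complete 12 weeks reads as a final stop, and the synopsis carries both versions. Nor does any sentence tell a site to keep these patients through V4.

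A reader might also infer that Appendix 1 flatly contradicts Sections 3.2 and 4.4.2.3. The documents do not support that. Footnote a qualifies week 15, and a full course agrees exactly. The conflict is confined to a patient on hold who never restarts.

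**Conclusion.** Wrong as written, and minor. The protocol states two treatment rules for patients who reach Hb ≥ 12 g/dL. Its last-dose rule, read literally, also places a patient off drug from V2 and not restarted at end of study near week 7, before V4, whether that patient is classed as discontinued or on hold. The week-7 result rests on weekly dosing from week 0 and on the V2 dose being withheld.

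A reader might go further and infer that week-12 values will be lost in responders, or that the response rate will be biased by some stated amount. The documents support neither. Appendix 1 schedules V3 and V4 for all patients, so loss is possible but not likely. The protocol gives no figure for how many patients reach 12 g/dL by V2. Section 3.3.1, which puts the usual improvement at 6 to 8 weeks, suggests few. If the SAP counts an earlier rise as response, a missing week-12 value need not change a patient's classification. No estimate of the effect on the primary result is therefore offered.

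**What to change.** 1. In Section 3.1.1 and the synopsis Description of Study, replace the stop sentence with: *If Hb reaches ≥ 12 g/dL, Recormon® is held until Hb ≤ 10 g/dL (see 4.2.2.1).*
2. In Sections 4.2.2.1 and 4.4.2, add: *Patients off Recormon® for Hb ≥ 12 g/dL attend all scheduled visits through V4 (week 12); their end-of-study visit is not before V4.*

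The cost is one sentence changed in two places and one sentence added in two. V3 and V4 are already scheduled for every patient, so no visit is added and the sample size is unchanged. Classification of the endpoint stays with the SAP.
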